## Handling of cross-over patients:

Date: 8 Apr 2024, Version 1.0

Patients with progressive disease on BI 1387446 monotherapy (Arm A) may cross over to the combination (Arm B) after completion of cycle 1 and will be treated at the highest dose level declared to be safe by the SMC at this time. Instead of completing the REP after monotherapy, these patients will continue treatment in combination by re-starting treatment at Cycle 1 Day 1 in Arm B (with limited set of screening assessments).

After crossing over from Arm A to Arm B, patients will be considered in the safety and efficacy analyses in Arm B. That is, if not specified otherwise, they will be included in the tabulation of safety and efficacy data of both arms. A footnote will be used in the outputs to indicate that cross-over patients are depicted in Arm A and Arm B.

In particular, for patients who cross over from Arm A to Arm B, two on-treatment periods will be defined, one for Arm A and a separate one for Arm B: The on-treatment period in Arm A will be derived as the time from first administration of BI 1387446 in Arm A until 90 days after the last administration in Arm A (including) or until the first administration of any trial drug in Arm B (excluding), whatever is first. The on-treatment period in Arm B will be derived as the time from first administration of study drug in Arm B until 90 days after the last administration of any trial medication. Figure 6.1: 1 provides a visualization of the two

[figure not shown]
Proprietary confidential information © 2024 Boehringer Ingelheim International GmbH or one or more of its affiliated companies.

on-treatment periods for a patient who crosses over to Arm B without completing the REP in Arm A.

The analyses of Arm A data will be presented by the patient's initial treatment in Arm A, the analyses of arm B data will be presented by the treatment the patient receives first after the crossover to Arm B.

For cross-over patients, the MTD evaluation period will only be defined for their treatment in Arm A.

Figure 6.1: 1 On-treatment periods and MTD evaluation period for cross-over patients

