3.1.1 Sequence of treatment arms and cohorts

A dose level of BI 1387446 will always be explored as single agent first. Only once determined to be safe as single agent, this dose of BI 1387446 will be used in combination with ezabenlimab (BI 754091), always lagging at least one dose level behind when administered in combination with BI 754091.

[figure not shown]

Figure 3.1.1: 1 Sequence of cohorts. BI446: BI 1387446, PD1: ezabenlimab (BI 754091).

Patients with progressive disease on BI 1387446 monotherapy (Arm A) may cross over to the combination (Arm B) after completion of cycle 1 and will be treated at the highest dose level declared to be safe by the SMC at this time. These patients will continue treatment in combination by re-starting treatment at Cycle 1 Day 1 in Arm B. These patients will be analysed in Arm A as long as treated with monotherapy. Instead of completing the REP after monotherapy, patients may cross over to Arm B without repetition of all screening procedures, but will have to undergo a limited set of assessments as specified in [Section 6.2.1](#). A minimum interval of 7 days must have elapsed between last dose of BI 1387446 in Arm A and first dose of ezabenlimab (BI 754091) or BI 1387446 in Arm B. Cross-over patients will be included together with other 'backfill patients' (patients enrolled to backfill cohorts at dose levels that do not exceed the MTD, see [Section 3.1.2](#) for details) in the safety and efficacy assessment in Arm B, but will not be considered for the main analysis of the MTD. For the main analysis of the MTD, cross-over patients will only be included while being treated with BI 1387446 monotherapy in Arm A. However, cross-over patients will be included in the sensitivity analyses of the MTD and thus be considered in addition (refer to [Section 7](#) for details).

Arm B will open at the starting dose level once the starting dose level in Arm A is considered safe by the SMC.

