3.2 DISCUSSION OF TRIAL DESIGN, INCLUDING THE CHOICE OF CONTROL GROUP(S)

Ezabenlimab (BI 754091) is expected to be required for efficacy due to the upregulation of PD-L1 following STING activation. This expectation is supported by internal and published preclinical data as well as clinical data on MK-1454 as monotherapy and in combination with pembrolizumab. Preclinical data for ADU-S100 indicate that the dose response relationship may be non-linear, possibly resulting in a decline in efficacy on non-injected lesions at higher doses. Thus, early combination with ezabenlimab (BI 754091) during dose finding is considered important for selection of a recommended dose for further development of BI 1387446.

In addition, a flexible enlargement of cohorts which have been confirmed to be safe by the SMC, the so called ‘backfill’ concept will be used to generate sufficient data at lower dose levels which appear relevant for dose selection and may only be identified during trial conduct.

BI 1387446 by its mode of action will increase cytokines, and thus has a potential risk to lead to cytokine release syndrome. Although there has been no increase of cytokines in preclinical

models for combination of BI 1387446 and ezabenlimab (BI 754091) compared to BI 1387446 alone, the trial design will ensure that a dose of BI 1387446 can only be tested in combination with ezabenlimab (BI 754091) if the same or a higher dose has been confirmed safe as monotherapy.

Dose escalation and cohort size will be determined based on the recommendation of the SMC, guided by a BLRM with overdose control. An escalation with overdose control design will increase the chance of treating patients at efficacious doses while reducing the risk of overdosing. This design is based on practical experience and is an efficient method due to its ability to identify the dose with a desired toxicity rate and its allocation of a greater proportion of patients to doses at, or close to, that desired dose [[R13-4802](#), [R13-4804](#), [R13-4805](#)]. The use of Bayesian models for Phase I studies has also been advocated by the EMA guideline on small populations [[R07-4856](#)] and by the FDA [[R13-4881](#)].

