7.5 DETERMINATION OF SAMPLE SIZE

No formal statistical power calculations to determine the sample size were performed for this trial.

For the dose escalation part, in Arm A and B, approximately 78 patients are expected to be enrolled based on the number of dose levels that are planned to be tested. That is, the planned number of patients for the individual treatment arms is approximately: 34 patients for Arm A and 44 patients for Arm B.

8. INFORMED CONSENT, TRIAL RECORDS, DATA PROTECTION, PUBLICATION POLICY, AND ADMINISTRATIVE STRUCTURE

The trial will be carried out in compliance with the protocol, the ethical principles laid down in the Declaration of Helsinki, in accordance with the ICH Harmonized Guideline for Good Clinical Practice (GCP), relevant BI Standard Operating Procedures (SOPs), the EU directive 2001/20/EC / EU regulation 536/2014 and other relevant regulations. Investigators and site staff must adhere to these principles. Deviation from the protocol, the principles of ICH GCP or applicable regulations as will be treated as “protocol deviation”.

Standard medical care (prophylactic, diagnostic and therapeutic procedures) remains the responsibility of the treating physician of the patient.

The Investigator will inform the sponsor immediately of any urgent safety measures taken to protect the trial patients against any immediate hazard, as well as of any serious breaches of the protocol or of ICH GCP.

The Boehringer Ingelheim transparency and publication policy can be found on the following web page: trials.boehringer-ingelheim.com. The rights of the Investigator and of the sponsor with regard to publication of the results of this trial are described in the Investigator contract. As a rule, no trial results should be published prior to finalisation of the CTR.

The certificate of insurance cover is made available to the Investigator and the patients, and is stored in the ISF.

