Similarly, Best percentage change from baseline in size of injected lesions (CTP version 1 and 2) and Best percentage change from baseline in size of injected target lesions (CTP version 3 and later) will be analyzed using descriptive statistics as well as waterfall plots. All lesion measurements recorded from start of trial treatment until the earliest of progression (confirmed intratumoral PD with CTP version 3 and later), start of subsequent anti-cancer therapy, loss-to follow-up or withdrawal of consent will be taken into account when calculating the best percentage change from baseline.

However, for the last two endpoints, special attention should be paid to the derivation of baseline, which will be determined according to the itRECIST publication: For each injected (target) lesion, the baseline is its diameter just before it is first injected, and the baseline SOD for injected lesions is the sum of these diameters, which may originate from different time points. The best response SOD is the SOD of these lesions at each lesion's smallest size after injection, again, possibly at different time points.

All secondary endpoints will be presented dose cohort, separately for Arm A and Arm B.

Proprietary confidential information © 2024 Boehringer Ingelheim International GmbH or one or more of its affiliated companies.

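### Arm B efficacy pools cross-over patients who progressed in Arm A with patients who started in Arm B, so any difference in response between the groups distorts the displayed dose-response and the Arm B total

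*SAP*

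**What the plan says.** **Who crosses.** SAP 6.1: "Patients with progressive disease on BI 1387446 monotherapy (Arm A) may cross over to the combination (Arm B) after completion of cycle 1". Every cross-over patient has therefore already progressed on the study drug as monotherapy.

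**At what dose.** The same section says that they "will be treated at the highest dose level declared to be safe by the SMC at this time". Their Arm B data are shown under the first treatment they receive after crossing.

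**How they are analysed.** "After crossing over from Arm A to Arm B, patients will be considered in the safety and efficacy analyses in Arm B". By default they appear in the efficacy tabulations of both arms, with a footnote saying so. Protocol 3.1.1 takes the same position for Arm B: "Cross-over patients will be included together with other" backfill patients.

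**How results are shown.** SAP 7.5.2: "All secondary endpoints will be presented dose cohort, separately for Arm A and Arm B". SAP 6.1 adds a total over all cohorts of an arm. ORR carries a Wilson 95% interval. Best percentage change is shown with descriptive statistics and waterfall plots, and response timing with swimmer plots.

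**How the MTD analysis differs.** Protocol 3.1.1 and the MTD set in SAP 6.4 keep cross-over patients out of Arm B in the main MTD analysis. They enter only the sensitivity or supplementary MTD analyses. The visible text makes no such split for efficacy.

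**The concern.** An Arm B cohort can contain two kinds of patient: those who started on the combination, and those who reached it after failing BI 1387446 alone. The mix is not the same at every dose. Starters added as backfill go to lower cleared levels (protocol 3.1.2), while cross-overs go to whichever level is the highest cleared on the day they cross. Protocol 3.1.2 also lets a level exceed its intended 8 patients to account for them. A comparison of pooled cohorts therefore mixes any dose effect with a difference in patient mix.

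This matters because activity by dose is something the protocol wants to read. Section 3.2 raises preclinical data on another STING agonist, "possibly resulting in a decline in efficacy on non-injected lesions at higher doses", and section 3.1.2 gives a non-linear dose-response as a reason for backfill. The Arm B total, the most likely single figure to be quoted, carries the same mixture.

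**Working it through.** **Inputs from the documents.** No plan figure depends on this point: "No formal statistical power calculations to determine the sample size were performed for this trial". Planned size is "34 patients for Arm A and 44 patients for Arm B"; 34 + 44 = 78, which agrees with the stated total. The intended maximum is 8 per dose level per arm (protocol 3.1.2). Protocol Table 10.5: 2 has six dose columns.

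**Inputs assumed.** True ORR p = 25% in starters at every dose, so there is no dose effect; ORR q = 5% in cross-overs; 8 starters per level; m cross-overs at a level. The documents give none of these rates or counts.

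**Formula.** Expected displayed ORR = (8p + mq)/(8 + m).

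**1. Cross-overs at one level only**, compared with a level that has none (25%):
- m = 2: (2.0 + 0.1)/10 = 21.0%, difference 4.0 points
- m = 4: (2.0 + 0.2)/12 = 18.3%, difference 6.7 points
- m = 8: (2.0 + 0.4)/16 = 15.0%, difference 10.0 points

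If the level with 4 cross-overs is the lowest one, the same 6.7 points appear as a rise with dose.

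**2. Rolling entry.** A simple simulation used 34 Arm A patients, six levels, Arm B lagging Arm A, 60% crossing, and crossing 3 to 12 weeks after entry. Mean cross-overs per Arm B level, low to high:
- 6 weeks per level: 1.9, 2.7, 3.2, 3.2, 3.0, 5.1
- 12 weeks per level: 2.3, 3.2, 3.2, 3.2, 2.5, 3.6

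They spread over all levels. At these means, lowest against highest level:
- 6 weeks: (2 + 0.095)/9.9 = 21.2% and (2 + 0.255)/13.1 = 17.2%; difference about 4 points
- 12 weeks: (2 + 0.115)/10.3 = 20.5% and (2 + 0.18)/11.6 = 18.8%; difference about 1.7 points

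With 30% crossing, the means at the lowest and highest levels are 0.97 and 2.52 (6 weeks) or 1.15 and 1.78 (12 weeks). The differences shrink to 22.8 − 20.2 = 2.6 and 22.5 − 21.4 = 1.1 points.

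**3. Varying q.** With q = 15%, m = 2, 4, 8 at one level gives 2.3/10 = 23.0%, 2.6/12 = 21.7% and 3.2/16 = 20.0%, a difference of 2 to 5 points. With q = p the displayed ORR is 25% whatever m is. With q > p every sign reverses.

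**4. Arm B total.** The 34 and 44 add to the patients entered, and a cross-over patient is entered once, so I read the 44 as starters. The 6-week, 60% run gives 19.1 cross-overs in all: (44 × 0.25 + 19.1 × 0.05)/63.1 = 18.9%, against 25% for starters. The sign here depends only on q against p, not on timing.

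**5. Noise.** One responder in 8 is 12.5 points. Wilson 95% intervals: 2/8 = 25% (7.1 to 59.1%); 2/12 = 16.7% (4.7 to 44.8%).

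**6. Chance of an apparent fall.** Exact binomial enumeration, true starter ORR 20% at both of two levels, 8 starters each. With no cross-overs, a fall and a rise have probability 37.5% each. With 4 cross-overs at the upper level, fall against rise is 60.4% against 32.4% (q = 0) or 52.4% against 39.9% (q = 10%). Unequal denominators also break ties, so the fair comparison is the same layout with q = 20%: 44.8% against 47.1%.

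**The case against.** **Direction.** A reader might infer that cross-overs always sit at the top dose and so produce a false fall in activity. The documents do not support that. The entry level is the highest cleared at the time of crossing, so it moves up with escalation, and an early cross-over enters what later becomes a low level. The distortion can run either way.

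**Size.** The 4 to 10 points compare a level that has cross-overs with one that has none, which is close to a worst case. The rates are assumed. Cross-overs also gain ezabenlimab, which protocol 3.2 expects to be needed for efficacy, so failure on monotherapy does not show how far response to the combination falls. Both objections stand, and the size has to be given as a range that includes zero.

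**Endpoint.** The decline in protocol 3.2 concerns non-injected lesions, whereas the arithmetic uses overall ORR, which includes injected lesions. Best percentage change in non-injected target lesions is the closer endpoint and is not quantified here. Waterfall plots show individual patients, but the visible text does not say that cross-overs will be identifiable in them.

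**Consequence.** A reader might infer that a recommended-dose decision is at risk. SAP section 4 states that development has been terminated, so no such decision is visibly pending; what remains is how the report is read.

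**Consistency.** The pooling is prespecified alike in both documents and disclosed by footnote. Leaving cross-overs out of the main MTD model serves DLT estimation and does not contradict including them for efficacy. That is fair, but a footnote does not let a reader recover the result in starters. The SAP default can be overridden elsewhere, and table shells or removed text might hold a split; none is visible.

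**Safety.** It is tempting to ask for the same split in the adverse event overview. No direction or size for a safety distortion has been shown, so that request is not made.

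**Conclusion.** The point holds as a matter of interpretability. Following the plan gives Arm B ORR and lesion-change results, by dose and in total, that mix two populations in proportions tied to calendar time, and no visible analysis separates them.

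With 25% against 5% and 8 starters per level, the spurious difference between levels is about 2 to 4 points under rolling entry with 60% crossing (less if fewer cross) and 4 to 10 points if 2 to 8 cross-overs fall at one level only. It is zero if the two groups respond equally. All of this lies well inside the Wilson intervals. The pooling is certain from the text; the bias depends on response rates and crossing times that the documents do not give. The documents do not establish a one-directional false decline, harm to a pending dose choice, or a safety distortion. What they support is a cheap improvement to how Arm B efficacy is reported.

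**What to change.** In SAP 6.1 and 7.5.2:
- Make patients who started in Arm B the main Arm B result for ORR and for best percentage change in injected and non-injected target lesions, by dose cohort and in total.
- Show cross-over patients in a separate column, with their number at each dose level.
- Flag them in the Arm B waterfall and swimmer plots.
- Keep the pooled figure as a labelled supplement.

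Align the sentence in protocol 3.1.1 that groups cross-over with backfill patients for efficacy. The cost is SAP wording, one extra column and a plot flag, with no new data. The downside is a smaller denominator, and so a wider interval, in the main column.

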In a telemetry study in Cynomolgus monkeys, a decline in contractility measured as LV dp/dtmax was observed at doses from [REDACTED]. The decline in contractility was not associated with a decline in blood pressure or an increase in heart rate.

Risk mitigation measures include

- exclusion of patients with cardiac insufficiency NYHA grade III or IV or a left ventricular ejection fraction of < 50 % from the trial ([Section 3.3.3](#)).
- detailed instructions for monitoring of vital signs (heart rate, blood pressure, [Sections 4.1.4.5](#) and [4.1.4.6](#)).
- assessment of cardiac biomarkers (e.g. troponin, natriuretic peptide, [Section 5.2.3](#))
- assessment of cardiac function by left ventricular ejection fraction ([Section 5.2.4](#))

Eye lens toxicity

In a repeated dose toxicity study in C57Bl/6 mice, increased incidences of diffuse subcapsular opacities in the anterior lens region were observed in males at [REDACTED] cycle and in females at [REDACTED] cycle at the end of treatment. Due to the absence of any histopathological findings in the lenses of all treated animals, the fact that spontaneous ocular pathologies are well known for C57Bl/6 mice ([R19-0517](#)), and taking into account that cytokines may be secondarily elevated in various inflammatory ocular diseases, but have not been reported to induce direct lenticular changes, these lens opacities are not considered to be unequivocally test item-related.

Risk mitigation measures include

- Exclusion of patients with absolute contraindications for cataract surgery
- Assessment of lens opacity using slit-lamp by an ophthalmologist at screening, at the 30-day safety follow-up, and at any time during the treatment period, if clinically indicated (refer to [Section 5.2.6](#)).

BI 1387446 in combination with ezabenlimab (BI 754091)

Combination of ezabenlimab (BI 754091) and BI 1387446 may lead to an increased rate and severity of irAEs compared to either drug alone, as is documented for combination of checkpoint inhibitors.

Preclinical data suggest that ezabenlimab (BI 754091) does not potentiate BI 1387446 mediated cytokine release. CRS to BI 1387446 and IRRs to ezabenlimab (BI 754091) may be

differentiated by the time of occurrence in relation to each drug administration, as IRRs to [REDACTED]

[REDACTED] overlap

cannot be excluded. Details for surveillance and medical management of CRS are included in [Section 4.1.4.6](#) and [Appendix 10.2](#).

Tumour biopsy

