7.2.5 Safety analyses

Adverse events will be coded using the Medical Dictionary for Drug Regulatory Activities (MedDRA). Standard BI summary tables and listings will be produced. All adverse events with an onset between start of treatment and 90 days after the last dose of trial medication will be assigned to the on-treatment period for evaluation.

All treated patients will be included in the safety analysis. In general, safety analyses will be descriptive in nature and will be based on BI standards. No hypothesis testing is planned.

Statistical analysis and reporting of adverse events will concentrate on treatment-emergent adverse events, i.e. all adverse events occurring between start of treatment and 90 days after the last dose of trial medication. Adverse events that start before first drug intake and deteriorate under treatment will also be considered as 'treatment-emergent'.

Frequency, severity, and causal relationship of adverse events will be tabulated by system organ class and preferred term after coding according to the current version of the Medical Dictionary for Drug Regulatory Activities (MedDRA) at database lock.

Laboratory data will be analysed both quantitatively as well as qualitatively. The latter will be done via comparison of laboratory data to their reference ranges and via assessment of CTCAE grades. Values defined as clinically relevant will be summarised. Treatment groups will be compared descriptively with regard to distribution parameters as well as with regard to frequency and percentage of patients with abnormal values or clinically relevant abnormal values.

Vital signs, physical examinations, or other safety-relevant data observed at screening, baseline, during the course of the trial and at the end-of-trial evaluation will be assessed with regard to possible changes compared to findings before start of treatment.

Other safety analyses (AESIs, centrally evaluated ECG, etc.) will be specified in detail in the TSAP.

[REDACTED]

[REDACTED]

[REDACTED]

[REDACTED]

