## 6. GENERAL ANALYSIS DEFINITIONS

## 6.1 TREATMENT(S)

In this Phase I trial treatments are not randomized. In Arm A and Arm B, different dose levels of BI 1387446 alone (Arm A) or of BI 1387446 in combination with 240 mg of ezabenlimab (Arm B) are being administered.

If not specified otherwise, all analyses will be performed for each treatment arm separately. Data will be presented by initial treatment, i.e. within each treatment arm for all dose cohorts separately and in total over all dose cohorts of that arm.

For safety summaries, events that start from the first administration of any trial medication until 90 days after the last administration of any trial medication (residual effect period, REP) will be assigned to the on-treatment period for evaluation. If not specified otherwise, all safety tables will be based on the on-treatment period. Adverse events that have an onset during the screening or the follow-up period will be displayed in separate listings from those that occurred during the on-treatment period.

The MTD evaluation period will be derived as the time from the first administration of study drug to the start of the second treatment cycle, i.e., in more detail as the time from the first administration of (any) trial medication to the start of the 2nd administration of ezabenlimab or 4th administration of BI 1387446 (whatever from the latter two comes first). In the case that the 2nd administration of ezabenlimab and/or the 4th administration of BI 1387446 are not given, the MTD evaluation period ends 90 days after the last administration.

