## 6.7 BASELINE, TIME WINDOWS AND CALCULATED VISITS

Unless otherwise specified baseline is defined as the time point closest to but prior to the first administration of any study medication. If no time is specified and the date is the same as the first administration date, then it will still be considered baseline if not specified otherwise. If there is no measurement earlier than the first administration of study medication, then no baseline will be derived.

For the analysis of 'Best percentage change from baseline in size of injected lesions' (CTP version 1 and 2) and 'Best percentage change from baseline in size of injected target lesions' (CTP version 3 and later) the derivation of baseline will follow the itRECIST publication, details are given in Section 7.5.2.

Study days and visits will be labelled according to the flowchart in the CTP.

Proprietary confidential information © 2024 Boehringer Ingelheim International GmbH or one or more of its affiliated companies.

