### Possible clinically significant abnormal laboratory values:

Possible clinically significant abnormal laboratory values are defined as those laboratory values that are of CTCAE grade  $\geq 2$  and show an increase from baseline value by at least one CTCAE grade. For those parameters for which no CTCAE grade has been defined, BI standard definitions will be used to determine possible clinical significance. Frequency of patients with possible clinically significant abnormal laboratory values will be provided whenever applicable. If no baseline value is available (or CTCAE grading at baseline cannot be assigned) but the patient has a post-baseline laboratory value of CTCAE grade  $\geq 2$ , an increase from baseline will be assumed, i.e. the laboratory value will be considered as possibly clinically significant.

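### The SAP gives cross-over patients no Arm B laboratory baseline, so an abnormality that arose on monotherapy and only persists can be tabulated as new in Arm B

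*SAP*

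**What the plan says.** **Periods.** SAP 6.1 counts safety events as on-treatment "until 90 days after the last administration of any trial medication (residual effect period, REP"). For cross-over patients it defines two periods that do not overlap. The Arm A period runs until "90 days after the last administration in Arm A (including) or until the first administration of any trial drug in Arm B (excluding"), whichever is first. For the second, "The on-treatment period in Arm B will be derived as the time from first administration of study drug in Arm B" and it ends 90 days after the last dose. These patients appear in the tables of both arms, and a footnote says so.

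**Timing.** Protocol 3.1.1 lets a patient with progression cross over after cycle 1 without completing the residual effect period: "A minimum interval of 7 days must have elapsed between last dose of BI 1387446 in Arm A" and the first Arm B dose of either drug. The patient restarts at Cycle 1 Day 1.

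**Baseline.** Under SAP 6.7, "baseline is defined as the time point closest to but prior to the first administration of any study medication". SAP 6.6 ties the laboratory baseline to the same moment. The only exception spelled out in 6.7 concerns the size of injected lesions.

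**Laboratory tables.** SAP 7.8.2 applies the same on-treatment periods as for AEs. It plans change from baseline, shifts in CTCAE grade from baseline to worst and to last value, and counts of possibly clinically significant abnormalities. The last are values of grade 2 or higher that "show an increase from baseline value by at least one CTCAE grade".

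**The concern.** The observation period restarts for Arm B but the reference value does not. For a cross-over patient, the literal Arm B laboratory baseline was taken before monotherapy began. Whatever changed during Arm A and is still present then appears in Arm B as a change on the combination.

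Protocol 7.2.5, in its paragraph on laboratory data, says "Treatment groups will be compared descriptively", so a reader of the trial report is invited to set the arms side by side. Cross-over patients are shown in Arm B at the dose they receive first after crossing, which is the highest declared safe at that time. A misplaced abnormality therefore lands in that cohort. A footnote that cross-over patients appear in both arms does not let the reader take them out again.

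**Working it through.** The documents give no figure for this point, so there is none to reproduce. The check applies the stated rules.

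**1. Which baseline applies?** SAP 6.7 and 6.6 both point to the period before the first dose of any trial drug. For a cross-over patient that dose is in Arm A. SAP 6.7 allows for other specifications, but neither the cross-over text in 6.1 nor 7.8.2 gives one for laboratory data.

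**2. Applying the SAP 7.8.2 rule.** A value counts if the worst grade in the period is at least 2 and (worst grade − baseline grade) is at least 1.

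| Grade before Arm A | Grade before first Arm B dose | Worst grade in Arm B | Pre-Arm A baseline | Pre-Arm B baseline |
|---|---|---|---|---|
| 0 | 2 | 2 | 2 − 0 = 2, counted | 2 − 2 = 0, not counted |
| 0 | 2 | 3 | 3 − 0 = 3, counted | 3 − 2 = 1, counted |
| 2 | 1 | 2 | 2 − 2 = 0, not counted | 2 − 1 = 1, counted |

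Row 1 is the problem case. The abnormality is also counted in Arm A, where it arose, so it is counted twice rather than moved. Row 3 shows that the literal baseline can also hide a genuine worsening in Arm B.

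**3. Scale (illustration).** Neither the number of cross-overs nor the share with a persisting abnormality is given. Assume 3 to 10 cross-overs and a share of 5% to 30%.
- Low end: 3 × 0.05 = 0.15 patients; 0.15/44 = 0.3 percentage points.
- High end: 10 × 0.30 = 3 patients; 3/44 = 6.8 points, or 3/54 = 5.6 points if cross-overs come on top of the planned 44.

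Tables are also shown by dose cohort. Protocol 3.1.2 intends at most 8 patients per dose level, so one miscounted patient among 8 is 1/8 = 12.5 points.

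**4. The Arm A window.** With a gap of g days between the last Arm A dose and the first Arm B dose, 90 − g of the 90 days fall in the Arm B period.
- g = 7 (the minimum): 83 days, 92.2%
- g = 14: 76 days, 84.4%
- g = 28: 62 days, 68.9%
- g = 42: 48 days, 53.3%

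Keeping the full 90 days in Arm A would not solve attribution. At the minimum gap the two periods would overlap for 83 days, and events on the combination would enter Arm A.

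**The case against.** **On the baseline.** The gap is one of silence. The SAP never says that Arm B shifts use the pre-Arm A value. Patients restart at Cycle 1 Day 1, so a programmer might take the Arm B value unprompted. The sponsor's laboratory standard is not available here, and the figure showing the two periods is missing from the text. This is fair as to what may happen in practice. But the SAP's explicit wording points to the pre-Arm A value, and that wording gives the wrong Arm B result.

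**On the window.** A reader might infer that the shortened Arm A window makes monotherapy harms count as combination harms and biases the comparison towards a more toxic combination, all the more since the protocol expects that the combination "may lead to an increased rate and severity of irAEs compared to either drug alone". The documents do not support that inference, for these reasons:
- The cut-off is deliberate and disclosed. It follows Protocol 7.2.1, which places these patients in Arm A while on monotherapy and in Arm B while on the combination.
- AEs are assigned by start date, so anything that starts before the first Arm B dose stays in Arm A.
- Later events occur under renewed BI 1387446 plus ezabenlimab, and timing alone cannot attribute them to monotherapy.
- The residual effect period of BI 1387446 itself is redacted, and 90 days is only the analysis window.
- Selection could work the other way, because cross-over patients have already completed at least one cycle of BI 1387446.

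**On safeguards.** Related AEs and SAEs are tabulated by drug. That helps for ezabenlimab, but it cannot separate Arm A from Arm B exposure to BI 1387446, which is given in both. The arms are not randomised, nothing is tested and development has ended. This limits the consequence to how the trial report reads.

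**Conclusion.** The laboratory baseline point holds on the SAP's wording. For cross-over patients, a grade 2 or higher abnormality that arose on monotherapy and only persists can be counted in Arm B as a shift and as a new possibly clinically significant abnormality, in addition to Arm A. The illustrated size, 0.15 to 3 patients, rests entirely on the assumed number of cross-overs and share with persisting abnormalities. It could be nil if few patients crossed over.

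The window rule is not an error and does not conflict with the protocol. It does mean that cross-over patients may have a much shorter Arm A follow-up and are then pooled in Arm B with patients who started there. Neither the size nor the direction of any effect on the AE tables can be determined from the documents.

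The main MTD analysis is not affected, because the MTD set takes cross-over patients only for Arm A. The optional supplementary model in SAP 7.4.4 uses on-treatment DLTs and includes cross-over patients, so only there could the split of periods matter.

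**What to change.** 1. In SAP 6.7 and 7.8.2, define a cross-over patient's baseline for the Arm B laboratory change, shift and possibly-clinically-significant tables as the last value before the first Arm B dose. Keep the present baseline for Arm A. The flow chart schedules safety laboratory tests at Cycle 1 Day 1, where these patients restart. If that sample is missing, the preceding value can be used, as SAP 6.6 already does.
2. In SAP 7.8, show the main Arm B safety tables with and without cross-over patients. Leave the on-treatment periods as they are.

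The cost is a few sentences of SAP text and some extra columns, with no new data. The drawback is small denominators, especially by dose cohort.
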